6. STUDY PROCEDURES

A. HISTORY TAKING, PHYSICAL EXAM AND PEANUT ORAL IMMUNOTHERAPY ADMINISTRATION

Please refer to 5.e for detailed description of study visits. In each study visit medical and allergy history will be reviewed (including dietary history) and physical exam will be performed before administering any treatment. Peanut OIT will be administered according to schedule provided in Table I and II.

B. SKIN PRICK TESTING (OPTIONAL)

Participants will have standard allergen skin prick tests (SPT) performed to peanut and possible other allergens based upon the subject's history and at the discretion of the investigator. The investigator will document in the database the rationale for performing the optional SPT. Examples include: checking mechanistic studies for subjects who develop specific gastrointestinal side effects (e.g. EoE), subjects who are unable to tolerate desensitization to 300 mg or subjects with severe adverse events.

If skin prick testing is scheduled for a certain visit, the participant will be notified prior leaving appropriate length of time to stop any antihistamines at the discretion of the investigator (5 half-lives of the antihistamine that is being used). A skin test probe is loaded with extract (Greer) then used to prick the epidermis. Positive (histamine) and negative (saline-glycerine) controls are placed as well to establish that the response is not blocked and to determine if there is dermatographism, respectively. The tests are read 15 minutes after placement, outlined in pen for wheal and flare and transferred by cellophane tape to paper to establish a record. SPTs are considered positive if there is a mean wheal diameter of 3 mm or greater, after subtraction of the saline control. Histamine wheals should be 3mm larger than the saline, and any saline wheel measuring larger than 3mm would invalidate the test and should be repeated.

C. BLOOD DRAW:

Venous blood may be obtained during the study for serum based assays (including but confined to serum peanut specific IgE). Blood drawn will be less than 2 ml/kg of body weight per visit up to a maximum of 45 ml in 8-week period for pediatrics and less than 550 ml in an 8-week period for adults. Blood collection will not occur more than 2 times per week.

D. SPIROMETRY

Spirometry will be done for every subject 7 years or older in screening visit.

Afterwards, if clinical indicated, spirometry will be administered per clinic asthma standard of care as an assessment of lung function in subjects 7 years of age or older during study visits. Procedures follow American Thoracic Society criteria. Bronchodilation is not conducted and beta-agonists do not need to be withheld prior to the test. The test is administered while the subject is in a standing position and using a nose clip. We will reference the Hankinson predictive values for lung function. Subjects between 7 and 11 years who are unable to perform spirometry will be offered an attempt to use a peak flow meter. Participants who are unable to maintain >80% PEFR of their predicted value will need to be evaluated by the NP or MD before proceeding.

E. SALIVA COLLECTION (OPTIONAL-SUBJECT TO THE INVESTIGATOR DISCRETION)

A 0.5 ml of saliva could be collected to run mechanistic assays as determined by the investigator. Examples include: checking mechanistic studies for subjects who develop specific gastrointestinal side effects (e.g. EoE), subjects who are unable to tolerate desensitization to 300 mg or subjects with severe adverse events.

Samples may be obtained by the subject spitting independently or the coordinator using a plastic syringe to gather saliva.

F. COMPLIANCE SHEETS

Subjects will be given sheets to record their compliance with the medication that needs to be changed on a weekly basis. The sheets will also include reactions the subjects have, the symptoms they experienced and how they were treated. Subjects will hand the sheets to their study coordinator at each visit and at the end of the study. The data from these sheets will be used to assess compliance and adverse events in addition to information gathered from subjects from their follow up surveys.

G. URINE PREGNANCY TEST

All participating females of child bearing age will have pregnancy urine test in screening then for the last follow up visit within 30 days of the last pregnancy test. Female subjects who become pregnant will be taken out of the study. Sexual abstinence will be accepted as an effective method of

contraception.

Sexually active female subjects are to use either:

- A highly effective method of birth control, defined as one that results in a low failure rate (i.e., less than 1 percent per year) when used consistently and correctly, such as implants, injectables, combined oral contraceptives, some intrauterine contraceptive devices (IUDs), sexual abstinence, or a vasectomized partner; or
- Alternatively, if a highly effective method of birth control is not used, an effective, double barrier method of contraception (e.g., male condom with female condom, cervical cap, diaphragm, or contraceptive sponge) may be used.

7. STUDY AGENT

A. FORMULATION, PACKAGING AND LABELING

Peanut flour will be packaged and labeled by the weight (mg) of the source material in each cup per dose at the University of North Carolina GMP manufacturing facility. Both the investigational drug as well as placebo (oat flour) are manufactured as described in Master File Type II MF2 15171.

B. PREPARATION, ADMINISTRATION AND DOSAGE

The investigational pharmacist will dispense the appropriate dose to the clinical staff. The peanut flour will be mixed into a food vehicle (applesauce, yogurt, or other tolerated food) for the subject to consume

C. STARTING DOSE AND ESCALATION SCHEDULE

Please refer to 5.E.

D. DOSE ADJUSTMENT

Please refer to 5.E, 5.F. and 5.G.

E. DURATION OF THERAPY

Total duration of therapy with peanut flour will be up to 6 months. This will be followed by 6 months of peanut equivalent.

F. RESCUE MEDICATION AND CONCOMITANT MEDICATION

Treatment of individual allergic reactions during OIT therapy will be with either an antihistamine and/or epinephrine, along with IV fluids, albuterol, and corticosteroids as indicated. Participants and parents are likely to have self-injectable epinephrine but for those who do not, self-injectable epinephrine will be prescribed in clinic. Participants will be trained in proper use of self-injectable epinephrine and will be able to demonstrate proper technique. All subjects will be given a food allergy action plan to follow while in this study.

8. SAFETY MONITORING

A. DEFINITIONS

Adverse Event (AE) or Medical Event

An adverse event is a new, undesirable medical event or occurrence or worsening of an existing condition (including an abnormal laboratory finding) in a subject that occurs during the study, whether or not it is considered to be study related. Adverse events or medical events and toxicities are treatment emergent signs and symptoms.

Serious Adverse Event (SAE)

A serious adverse event is defined as any adverse therapy experience occurring at any dose that suggests a significant hazard, contraindication, side effect, or precaution. This includes, but may not be limited to any of the following events: (This terminology is from Section B.2 on the FDA MedWatch form. For a copy of the current MedWatch Form 3500, see the list of PDF forms on the Web at <http://www.fda.gov/opacom/morechoices/fdaforms/cder.html>)

- 1) Death: A death occurring during the study or which comes to the attention of the investigator during the protocol-defined follow-

up after the completion of therapy whether or not considered treatment-related, must be reported.

- 2) Life-threatening: Any adverse therapy experience that places the subject or subjects, in the view of the investigator, at immediate risk of death from the reaction as it occurred (i.e., it does not include a reaction that, had it occurred in a more serious form, might have caused death)
- 3) In-patient hospitalizations.
- 4) Persistent or significant disability or incapacity.
- 5) Congenital anomaly/birth defect.
- 6) An event that required intervention to prevent permanent impairment or damage

Unexpected Adverse Events

An adverse event is considered “unexpected” when its nature or severity is not consistent with the descriptions in the protocol or informed consents.

For subjects who become pregnant during the study and whom we will withdraw from the study as stated above, we will continue to monitor them with phone calls every 3 months until delivery. We will use our phone interview questionnaire to report any adverse outcomes for these subjects and report the outcome of all pregnancies in our study report.

B. TOXICITY GRADING

Symptoms associated with systemic allergic reactions and/or anaphylaxis that occur during administration of peanut flour or peanut equivalent food will be graded according to table below, that was adapted from the grading of allergic reactions in the following article:


Grade 1 Mild	Grade 2 Moderate	Grade 3 Severe	Grade 4 Life threatening	Grade 5 Death
Transient or mild discomforts (< 48 hours), no or minimal medical	Symptoms that produce mild to moderate limitation in activity some assistance may be needed; no or	Marked limitation in activity, some assistance usually required; medical intervention/therapy	Extreme limitation in activity, significant assistance required; significant	Death

intervention/therapy required. These symptoms may include pruritus, swelling or rash, abdominal discomfort or other transient symptoms.	minimal intervention/therapy is required. Hospitalization is possible. These symptoms may include persistent hives, wheezing without dyspnea, abdominal discomfort/ increased vomiting or other symptoms	required, hospitalization is possible. Symptoms may include bronchospasm with dyspnea, severe abdominal pain, throat tightness with hoarseness, transient hypotension among others. Parenteral medication(s) are usually indicated.	medical/therapy. Intervention is required; hospitalization is probable. Symptoms may include persistent hypotension and/or hypoxia with resultant decreased level of consciousness associated with collapse and/or incontinence or other life threatening symptoms.	
---	--	---	---	--

Other adverse events related to study procedures other than peanut flour or peanut equivalent and adverse events that are not associated with study procedures will be graded according to the criteria in the National Cancer Institute NCI –CTC, as following:

Grade 1 Mild

Transient or mild discomforts (< 48 hours), no or minimal medical intervention/therapy required, hospitalization not necessary (non-prescription or single-use prescription therapy may be employed to relieve symptoms, e.g., aspirin for simple headache, acetaminophen for post-surgical pain).

Grade 2 Moderate

Mild to moderate limitation in activity some assistance may be needed; no or minimal intervention/therapy required, hospitalization possible.

Grade 3 Severe

Marked limitation in activity, some assistance usually required; medical intervention/therapy required, hospitalization possible.

Grade 4 Life-threatening

Extreme limitation in activity, significant assistance required; significant

Grade 5 Death	medical/therapy intervention required, hospitalization or hospice care probable.
	Death.

Anaphylaxis:

Anaphylaxis will be defined according to second National Institute of Allergy and Infectious Disease/ Food Allergy and Anaphylaxis Network symposium (Sampson H, Muñoz-Furlong A, Campbell R, *et al.* 2006. Second symposium on the definition and management of anaphylaxis: Summary report: Second National Institute of Allergy and Infectious Diseases/Food Allergy and Anaphylaxis Network symposium. *J Allergy Clin Immunol*. 92:397–403) as following:

Table I. Clinical criteria for diagnosing anaphylaxis

Anaphylaxis is highly likely when any one of the following 3 criteria are fulfilled:

1. Acute onset of an illness (minutes to several hours) with involvement of the skin, mucosal tissue, or both (eg, generalized hives, pruritus or flushing, swollen lips-tongue-uvula)

AND AT LEAST ONE OF THE FOLLOWING

a. Respiratory compromise (eg, dyspnea, wheeze-bronchospasm, stridor, reduced PEF, hypoxemia)

b. Reduced BP or associated symptoms of end-organ dysfunction (eg, hypotonia [collapse], syncope, incontinence)

2. Two or more of the following that occur rapidly after exposure **TO A LIKELY ALLERGEN FOR THAT PATIENT** (minutes to several hours):

a. Involvement of the skin-mucosal tissue (eg, generalized hives, itch-flush, swollen lips-tongue-uvula)

b. Respiratory compromise (eg, dyspnea, wheeze-bronchospasm, stridor, reduced PEF, hypoxemia)

c. Reduced BP or associated symptoms (eg, hypotonia [collapse], syncope, incontinence)

Anaphylaxis is highly likely when any one of the following 3 criteria are fulfilled:

- d. Persistent gastrointestinal symptoms (eg, crampy abdominal pain, vomiting)
- 3. Reduced BP after exposure to **KNOWN ALLERGEN FOR THAT PATIENT** (minutes to several hours):
 - a. Infants and children: low systolic BP (age specific) or greater than 30% decrease in systolic BP*
 - b. Adults: systolic BP of less than 90 mm Hg or greater than 30% decrease from that person's baseline

PEF, Peak expiratory flow; **BP**, blood pressure.

* Low systolic blood pressure for children is defined as less than 70 mm Hg from 1 month to 1 year, less than (70 mm Hg + [2 × age]) from 1 to 10 years, and less than 90 mm Hg from 11 to 17 years.

Eosinophilic Esophagitis:

We will monitor subjects for the development of eosinophilic esophagitis using Modified Aceves Questionnaire for all of our patients. The questionnaire will be done at screening, then visits 4,6,9,10,11 and 12. The answers in the questionnaire will be scored and those who have a score of 5 or more will be evaluated for possible Eosinophilic Esophagitis and will be referred to gastroenterology

C. RELATIONSHIPS TO PROCEDURE DEFINITIONS

Associated: There is a reasonable possibility that the adverse event may have been caused by the test product and/or procedure. This definition applies to those adverse events that are considered definitely, probably or possibly related to the procedure.

1) Definitely related: An adverse event that follows a temporal sequence from administration of the test product and/or procedure; follows a known response pattern to the test article and/or procedure; and, when appropriate to the protocol, is confirmed by improvement after stopping the test product (and by

reappearance of the reaction after repeat exposure); and cannot be reasonably explained by known characteristics of the subject's clinical state or by other therapies.

2) **Probably related:** An adverse event that follows a reasonable temporal sequence from administration of the test product and/or procedure; follows a known response pattern to the test product and/or procedure, is confirmed by improvement after stopping administration of the test product or stopping the procedure; and cannot be reasonably explained by the known characteristics of the participant's clinical state or other therapies.

3) **Possibly related:** An adverse event that follows a reasonable temporal sequence from administration of the test product and/or procedure and follows a known response pattern to the test product and/or procedure, but could have been produced by the participants' clinical state or by other therapies.

Not associated: An adverse event for which sufficient information exists to indicate that the etiology is not related to the test product and/or therapy.

Unrelated: An adverse event that does not follow a reasonable temporal sequence after administration of the test product and/or procedure; and most likely is explained by the participant's clinical disease state or by other therapies. In addition, no change in a reaction with stopping or restarting the test product or procedure would support an unrelated relationship.

For additional information and a printable version of the NCI-CTCAE manual, consult the NCI- CTCAE website,

<http://ctep.cancer.gov/reporting/ctc.html>.

D. ADVERSE EVENTS COLLECTION PROCEDURES

The Principal Investigator is responsible for collecting and recording all clinical data. As these results are collected, all toxicities and adverse events will be identified and reported as described above. The Principal Investigator will determine relationship of the event to the study activities and decide the course of action for the study participant.

Adverse events will be evaluated from the onset of the event until the time the event is resolved or medically stable or until 30 days after reporting of the event, whichever comes first.

Adverse events may be discovered through any of these methods:

1. Observing or questioning the participant during study visits.
2. Reviewing the forms given to the patient for home monitoring and documenting compliance.
3. Receiving an unsolicited complaint from the participant.

E. SERIOUS ADVERSE EVENT NOTIFICATION

The research staff will notify the principle investigator of any serious adverse event immediately on learning about the event. Serious adverse events will be recorded on the adverse event CRF within 24 hours of their occurrence. The following attributes must be assigned:

- Description
- Date of onset and resolution (if known when reported)
- Severity
- Assessment of relatedness to test procedure
- Action taken

The principal investigator must apply their clinical judgment to determine whether an adverse event is of sufficient severity to require that the subject be removed from treatment. If necessary, an investigator must suspend any trial procedures and institute the necessary medical therapy to protect a subject from any immediate danger.

Subsequent review by the DSMB or IRB may suspend further treatment or procedures. The DSMB retain the authority to suspend additional enrollment and treatments as applicable.

A subject may also voluntarily withdraw from the study due to what he/she perceives as an intolerable adverse event, or for any other reason. If

voluntary withdrawal is requested, the subject should be asked to complete a study termination form, and be given appropriate care under medical supervision until the symptoms of any adverse event resolve or their condition becomes stable.

F. NOTIFYING THE IRB AND DSMB

A Data Safety Monitoring Board (DSMB) will monitor the study for safety. The DSMB will meet periodically to review accruing safety data. The committee will consist of individuals with clinical study experience drawn from the fields of clinical immunology (specifically food allergies) and biostatistics. These individuals will be entirely independent of the conduct of the study.

The study investigator will provide the DSMB with listings of all AEs/SAEs on a periodic basis. The DSMB will meet annually to review all AEs/SAEs. Furthermore, the DSMB will be informed of all SAEs within 24 hours. Furthermore, the sponsor will inform the FDA, IRB, and DSMB of expedited reports of SAEs.

G. REPORTING CRITERIA

The investigator will ensure the timely dissemination of all AE information, including expedited reports, to the IRB in accordance with applicable local regulations and guidelines.

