5. STUDY DESIGN AND SCHEDULE

A. LOCATION

Visits will be done at the University of North Carolina-Chapel Hill Food Allergy Study Center (FASC), located in the CTRC building. The FASC is equipped as a clinic. In addition to MD and NP coverage, there are 24-hour adult and pediatric rapid response teams in case of emergencies. The study

site is adjacent to the UNC Hospitals Emergency Department where subjects can be transferred for continued monitoring and acute care as needed.

B. DURATION OF ENROLLMENT

The study enrollment duration is for 2 years or until a commercial peanut OIT products is available to participants whichever is sooner.

C. DURATION OF THE STUDY PER PARTICIPANT

Each participant will be in the study for a total of 12 months. There will be three phases in the study: escalation phase for 1 day, build up phase up to 16 weeks, and maintenance phase up to 3 months on peanut OIT followed by 6 months of food equivalent to tolerated peanut protein.

D. STUDY VISITS

Participants will have: an initial study visit (screening), followed by one visit for the escalation phase, followed by visits every 1-2 weeks for the up dosing phase, a visit at the end of peanut OIT treatment at 6 months, a phone interview at 9 months and a final visit at the end of the study at 12 months. The screening visit may be combined with the initial escalation visit.

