3. BUILD UP PHASE

After the first day of desensitization, subjects will return to the research unit the following day to begin the build-up phase of the study. The subject will ingest 6 mg, or a lower amount based on the reaction during the escalation phase. After the subject is observed for a minimum of 30 minutes for symptoms to the study protein ingestion, he or she will be discharged from the research unit and will continue to consume the study protein at home daily fourteen days (-3/+7 days). The family receives the study protein doses as a powder that they give to the child each day by sprinkling it on a previously tolerated food (e.g., apple sauce). Subsequently, subjects will return to the clinical research unit every 2 weeks (-3/+7 days) to monitor their adherence to the dosage administration and increase the dose to the next escalation amount (Table II). Vital signs are performed prior to the dose administration, prior to the completion of the observation period before discharge, and anytime symptoms occur. If the study team feels that a longer observation time is warranted based on the prior dosing history of the subject or their current physical status, the subject will be observed for a longer period of time. If symptoms occur that do not require treatment, the subject will

be observed until they resolve. If symptoms occur that require diphenhydramine or albuterol, the subject will be observed a minimum of 2 hours or until symptoms resolve. If symptoms occur that require epinephrine, the subject will be observed at least 4 hours or until symptoms resolve. If symptoms do not fully resolve after 6 hours or if new symptoms occur, the subject will be transferred to UNC Children's Hospital to be observed overnight. Per individual stopping rules, participants experiencing severe symptoms during buildup will be terminated from the study.

Subjects who tolerate dose escalations will take that dose daily for a period 2 weeks (-3/+7 days) after which they will return to the clinical research unit to have the daily dose increased proportionately at each visit until the maximum daily dose of study protein (300 mg) is reached. Mechanistic studies may be done at the discretion of investigator to address any clinical symptoms for further studies.

Table II

Dose #	Dose	Interval(weeks)
5	6mg	Day 2
6	12mg	2
7	25mg	2
8	50mg	2
9	75mg	2
10	100mg	2
11	150mg	2
12	225mg	2
13	300mg	2

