5. PEANUT FOOD EQUIVALENT PHASE

At the end of maintenance peanut OIT phase, subjects will be given instruction during their last study visit in maintenance phase to start a peanut food equivalent of 300 mg peanut protein: which include the following options: peanuts (not dry roasted), peanut butter, powdered peanut butter, mini snickers, mini Reese's cup, cheese peanut butter crackers, Reese's pieces, Reese's peanut butter chips or Goober. An instruction sheet will be provided on how much to take of one of these products on a daily basis. This phase will last for 6 months. During this phase, subjects will continue to fill compliance sheets and they will receive phone calls from study coordinators at 9 months. This will be no study visits until the end of this phase to hand daily compliance sheets and fill a survey. At the end of the study the subjects may have the option to enroll in our peanut OIT follow up study if study investigator deemed they meet inclusion criteria for the study.

E. HANDLING ADVERSE REACTIONS AND FOLLOW UP DURING HOME DOSING

Each subject is given multiple ways to contact study staff when they are enrolled in the study. This is reviewed at the end of each visit. The families are told to contact the study staff if they have any questions or concerns before the next visit or at any time during the study. Study contact information given to families include the research clinic phone number, email addresses and office numbers of the, study coordinators, and instructions for how to get in contact with the pediatric on-call allergist who can reach the lead coordinator if needed. Subjects who have any symptoms during observed dosing, or those who express any specific concerns are given a follow up phone call on the day after dose escalation. All subjects will be asked to carry an auto-injector epinephrine. If prescription is not provided by their physician, we will provide them with a prescription for an auto-injector epinephrine. We will ask subjects to fill their prescription and

bring their epinephrine auto-injector with them before starting treatment to verify they have filled their prescription.

F. MANAGING MISSED DOSES

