Aim 2. Characterize and compare the two stages of the protocol in terms of safety and compliance.

We will rely on the following methods to accomplish Aim 2:

1. Our main analyses will focus on stage-specific estimates of incidence rates of adverse events and the proportion of days of treatment missed.

Comparisons of the two stages will rely on logistic regression models for rates, and generalized log-linear models for counts of days. The primary emphasis will be on point estimates and confidence interval estimates. No hypothesis tests will be performed.

2. Our secondary analyses will include estimation of

- the stage-specific incidence rates of gastrointestinal AEs during the entire 2-stage treatment sequence.
- the stage-specific incidence rates of Epipen use
- the stage-specific incidence rates of drop-outs due to gastrointestinal AEs.

Comparisons of the two stages will rely on logistic regression models for rates, and generalized log-linear models for counts of Epipen usages. The primary emphasis will be on point estimates and confidence interval estimates. No hypothesis tests will be performed.

3. Exploratory analyses will be used to investigate potential candidate risk factors for AEs (using logistic regression models) and causes of missed treatment days (using generalized log-linear models for counts of days).

4. Descriptive tabular and graphical methods will be used to visualize the data and examine the relationships among the measures of interest using graphical and descriptive methods.

Statistical estimates of interest include stage-specific parameter estimates (e.g., incidence rates) as well as estimates of differences between stage-specific parameters (e.g., odds ratios, or rate differences). All statistical estimates will be tabulated with the corresponding 95% confidence intervals (CI). Interpretation of these CIs will be an integral part of analysis. For Aim 2, sensitivity analyses will be performed to evaluate the robustness of the main

results to reasonable perturbations of the choices of statistical methods and statistical assumptions used.

Aim 3. Explore the mechanisms responsible for long-term desensitization and/or tolerance to food allergens induced by immunotherapy.

We will rely on the following methods to accomplish Aim 3:

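### The EoE questionnaire is scheduled by undefined visit numbers, and on any count of the planned visits it falls mostly in the OIT stage, with at most one clinic administration in the food stage

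*Combined protocol and SAP*

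**What the plan says.** Section 8.B (Toxicity Grading, under Eosinophilic Esophagitis) sets the timing: "The questionnaire will be done at screening, then visits 4,6,9,10,11 and 12". It attaches an action to the result: "those who have a score of 5 or more will be evaluated for possible Eosinophilic Esophagitis", with referral to gastroenterology.

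No visit-number key appears in the supplied text, so the numbers have to be inferred from Section 5. Section 5.D (Study Visits) describes "an initial study visit (screening), followed by one visit for the escalation phase", then up-dosing visits, a visit at the end of OIT at 6 months, a phone interview at 9 months and a final visit at 12 months. It adds: "The screening visit may be combined with the initial escalation visit". The build-up subsection requires a further attendance on the day after escalation: "subjects will return to the research unit the following day to begin the build-up phase of the study". The food-equivalent subsection plans no clinic visit until the end of that phase; in between, "they will receive phone calls from study coordinators at 9 months".

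Section 10.B, Aim 2, lists among its secondary estimates "the stage-specific incidence rates of gastrointestinal AEs during the entire 2-stage treatment sequence" and the stage-specific rates of drop-out due to GI adverse events, and it compares the two stages. Section 4.D, item 4, includes EoE among the events that count toward suspension of the study.

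**The concern.** A comparison of adverse event rates between two periods is only as fair as the effort made to find events in each. Here a scored GI symptom screen, with a referral attached, is given repeatedly in the first stage and rarely in the second. GI events that come to light because someone asked will tend to be found more often on OIT than on food. That could make the move to food look gentler on the gut than it is, on a question that Section 1.B says has not been well studied.

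There is a second, practical problem. A schedule written in visit numbers that nobody has defined can be applied in more than one way. Whether the 12-month visit carries a questionnaire depends on how the site counts.

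**Working it through.** **Check on the visit count.** Table II has eight increases after the Day 2 dose (12, 25, 50, 75, 100, 150, 225 and 300 mg), each at a 2-week interval. 8 × 2 = 16 weeks, which reproduces the maximum build-up length in Section 5.C. Eight up-dosing visits is therefore the plan's own number.

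**Clinic visits in order** (Sections 5.D, 5.D.3 and 5.D.5; the 9-month phone interview is not counted as a visit):

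- Screening numbered separately: screening 1 + escalation 1 + Day 2 1 + up-dosing 8 + end of OIT 1 + final 1 = 13 visits.
- Screening unnumbered, or combined with escalation: 13 − 1 = 12 visits.

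**Where the listed visits fall:**

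| Listed visit | Screening unnumbered or combined | Screening is a separate visit 1 |
|---|---|---|
| 4 | 25 mg | 12 mg |
| 6 | 75 mg | 50 mg |
| 9 | 225 mg | 150 mg |
| 10 | 300 mg | 225 mg |
| 11 | end of OIT | 300 mg |
| 12 | 12-month final visit | end of OIT |
| OIT v food | 5 v 1 | 6 v 0 |

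The baseline questionnaire at screening is left out of both counts. In the left column, an additional OIT visit that took a number (for example after missed doses, Section 5.F) would push the final visit to 13 and turn 5 v 1 into 6 v 0.

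**A bound that does not need the table.** The food stage has at most one clinic visit. If all six listed visits are clinic visits that take place, at least 6 − 1 = 5 fall in OIT.

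**Other conventions.** If Day 2 is not numbered and screening is unnumbered or combined, there are 1 + 8 + 1 + 1 = 11 clinic visits. The split is then 4 v 1 with visit 12 non-existent, or 4 v 2 if the phone interview takes a number. Numbering from 0 with screening combined and Day 2 omitted lowers OIT to 3, with 1 or 2 in food and at least one listed visit that does not exist. No convention tried puts more than two administrations in the food stage, or more than one in clinic, and all of them place more in OIT.

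**Rate over the nominal stages of 6 months each.** 5 v 1 is 5/6 = 0.83 against 1/6 = 0.17 per month. 6 v 0 is 1.0 against 0 per month.

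**What cannot be calculated.** The documents give no yield per questionnaire, no recall period and no expected GI event rate, so the imbalance cannot be turned into a bias in a rate or an odds ratio.

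**The case against.** The strongest reply is that the counts are inferred. The protocol refers to appendices that were not supplied, and a visit key may sit in one of them. Section 8.B names screening apart from the numbered visits, which fits a fixed numbering that ends at the 12-month visit. A reader might infer that 6 v 0 is the plan, that some participants are never screened after month 6, or that screening differs from one participant to the next. The documents do not establish any of these. They would follow only if screening were numbered as a visit or numbers were reassigned per participant. With fixed labels, combining screening with escalation shifts nothing. This part of the objection stands.

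A 4 v 2 reading is also possible, and it would mean that months 9 and 12 are already covered. It stands less well: it has to leave out the Day 2 attendance that the build-up subsection requires and number as a visit a phone interview that Section 5.D lists as something else.

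On consequences, a reader might infer that food must look safer whatever the truth, or that EoE arising on food would go undetected. Neither is supported. The questionnaire is an EoE referral screen and is not named among the adverse event discovery routes in Section 8.D. Compliance sheets recording symptoms run through both stages (Sections 5.D.5 and 6.F). Section 4.C, item 3, refers anyone with compatible symptoms, at any stage. The food stage also has the 9-month call and an end-of-study survey.

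Finally, denser screening while doses are rising is a defensible choice, and Aim 2 is estimation without hypothesis tests. Both are true. But estimates with confidence intervals are still read as a comparison, and the intervals do not reflect unequal ascertainment.

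**Conclusion.** The concern holds in a limited form. The questionnaire is tied to visit numbers that the supplied text leaves undefined, and most post-baseline administrations fall in the OIT stage, with at most one in clinic in the food stage. The best-fitting count is 5 v 1, which leaves six months between the end-of-OIT questionnaire and the next one. The count is 6 v 0 if screening is a separate visit 1. These figures assume that Day 2 is numbered, the phone interview is not, and no extra visit takes a number.

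One solicited channel for GI symptoms is therefore unequal between the stages that Aim 2 compares, and it may bias the comparison toward fewer GI events on food. The likely direction can be argued from the design; the size cannot be computed. GI ascertainment on food is thinner, not absent. This is an inexpensive improvement that should be made, not a flaw that invalidates the stage comparison.

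**What to change.** In Section 8.B:

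- Replace the visit numbers with named time points (dose level or study month) that read the same whether or not screening is combined with escalation. If a visit key exists, cite it.
- State that the 12-month final visit is included for every participant.
- Add the questionnaire to the 9-month phone interview that is already scheduled.

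If the OIT administrations stay as they are, the split moves from 5 v 1 to 5 v 2 (or from 6 v 0 to 6 v 2), and the longest planned interval without the questionnaire in the food stage falls from six months to three. The stages would still be unequal. Section 10.B, Aim 2, should therefore say that the remaining difference in ascertainment will be noted when the stage-specific GI rates and GI drop-outs are interpreted.

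The cost is a wording change, one short questionnaire in an existing call, and possibly a few more referrals. No new visit is needed.
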